4.2. Discussion of Study Design, Including Choice of Control Group

A randomized, double-blind, placebo-controlled study design was chosen to investigate the effects of IW-3300 administered once daily for 7 days as a low-volume enema. Subjects will be randomized within each cohort to ensure that the treatment groups are comparable and to minimize the potential for selection bias. The study will be double-blind to ensure that the subjects and CRU staff are unaware of the treatment assignment and to minimize the potential for bias in study assessments or AE reporting. Placebo was chosen as the control so that the rate of spontaneously occurring AEs can be determined and to reduce the potential for bias in the reporting of AEs.

To ensure a thorough assessment of safety, subjects will be confined to the CRU for the duration of the Clinic Period, from Check-in (Day -1) through until Discharge (Day 8), which will occur after completion of the assessments (at least 24 hours after administration of study drug) and at the investigator's discretion. CRU staff will contact subjects for the Follow-up Phone Call on Day 21 (+3), conducted 14 days after the last dose, for safety follow-up; at the discretion of the investigator, subjects may be requested to return to the CRU for their follow-up contact.

To evaluate any effects of IW-3300 on bowel and bladder function, subjects will complete the bowel movement (BM) portion of the bladder and bowel movement diary (BBMD) on 7 consecutive days during the Screening Period to establish a baseline for bowel function without study drug. Similarly, subjects will provide answers to the bladder/urinary-symptom-related questions in the BBMD predose on Day 1, with a 24-hour recall, to establish a baseline without study drug.

Because this is the first multiple-dose study with IW-3300 in humans, cohorts will be enrolled sequentially, following a safety review of prior dosed cohort(s) by a Dose Escalation Committee ([Protocol Section 6.6](#)). In addition, stopping criteria have been established to ensure that dosing at the same or higher dose levels will stop should a safety signal be detected ([Protocol Section 7.1.1](#)). In this case, a lower dose of IW-3300 could be used.

4.3. Method of Assigning Subjects to Treatment Groups

Randomization numbers encoding the subjects' treatment assignments will be based on a randomization schedule that is computer-generated; the randomization schedule will be generated prior to the study, by an independent statistician from a CRO who is not otherwise associated with the study.

4.4. Blinding

The investigator and all other CRU staff, sponsor study personnel, and the subject will remain blinded to individual subject treatment assignments throughout the study, except as noted below.

The Dose Escalation Committee, which will include sponsor and CRO representatives, will conduct blinded reviews of all the safety/tolerability parameters of the dosing cohort through Discharge (Day 8) in order to make decisions regarding subsequent dosing.

Specific designated personnel in the Ironwood Global Patient Safety Group may be unblinded to the treatment assignment of individual subjects for regulatory reporting purposes. All other

sponsor study personnel, except as described, will remain blinded until the study is complete and the database is locked, unless warranted by emerging safety or tolerability issues.

Specifically designated unblinded CRU pharmacy staff will be responsible for preparing dosing for each cohort and providing doses to the study coordinator to administer to subjects. The investigator (except as detailed in the next paragraph) and the remaining CRU staff will be blinded as to treatment. In the event of a Quality Assurance audit, the auditor(s) will be allowed access to unblinded study intervention records at the CRU to verify that randomization / dispensing has been done accurately.

Site unblinding of a subject's treatment assignment is restricted to emergency situations that necessitate identifying the study drug for the welfare of the subject. Subject safety must always be the first consideration in making such a determination. If the investigator decides that unblinding is warranted, the investigator, or person designated by the investigator, should contact the sponsor's medical monitor directly to discuss the need for emergency unblinding. Individual sealed unblinding envelopes, which can be opened to identify the treatment assignment for an individual subject in an emergency, will be provided to and retained by the CRU pharmacist. The reason for breaking the blind will be recorded.

4.5. Sample Size and Power Considerations

No statistical sample size determination process was performed. The sample size chosen for each cohort (9 subjects) is considered sufficient for evaluation of safety, tolerability, PK, and microbiome.

5. STATISTICAL ANALYSIS SETS

5.1. Screened Set

The Screened Set consists of all subjects who signed the informed consent.

5.2. ITT Set

The ITT Set consists of all subjects in the Screened Set who have been randomized to a treatment regimen. Analysis will be performed according to the allocated treatment regimen regardless of the treatment regimen actually received.

5.3. Safety Analysis Set

The Safety Analysis Set consists of all subjects who received any amount of study drug. Analysis will be performed according to the treatment actually received regardless of the allocated treatment.

5.4. PK Analysis Set

The PK Analysis Set consists of all subjects in the Safety Analysis Set who have at least 1 postdose PK assessment. Analysis will be performed according to the treatment actually received regardless of the allocated treatment.

5.5. Microbiome Analysis Set

The Microbiome Analysis Set consists of all subjects in the Safety Analysis Set who have at least 1 postdose microbiome assessment. Analysis will be performed according to the treatment actually received regardless of the allocated treatment.

6. STUDY SUBJECTS

All subjects on placebo arm will be pooled from available cohorts, whenever appropriate, to conduct analyses.

6.1. Disposition of Subjects

The number and percentage of subjects who were included in the Screened, ITT, Safety or Microbiome analysis sets will be summarized by treatment group (or cohort) and overall, except for the Screened Set, which will only be summarized overall.

Some subjects may withdraw from the study prior to completion of the Clinic Period, or may discontinue study drug before study day 7. The number and percentage of subjects who completed or who prematurely discontinued from the study or from study drug will be presented for each treatment group (or cohort) and overall for the Safety Analysis Set. Reasons for premature discontinuation as recorded either on the termination page of the eCRF or on the adverse event eCRF will be summarized (number and percentage) by treatment group (or cohort) and overall.

6.2. Demographic and Other Baseline Characteristics

Descriptive summaries of demographic and baseline characteristics will be presented by treatment group (or cohort) and overall, for the Safety Analysis Set.

The following demographic characteristics will be summarized in the tables: age (years and by category), sex, ethnicity, race, weight, height, and BMI.

6.3. Medical and Surgical History

Medical and surgical history will be collected at the Screening Visit and will be coded using MedDRA Version 24.0. A data listing will be provided for the Safety Analysis Set.

The medical history will be summarized by system organ class (SOC) and preferred term (PT) for each treatment group and overall, for the Safety Analysis Set.

6.4. Prior Medications, Therapies, Procedures

Prior medications will be coded using the WHO Drug Dictionary dated Sept 2021. Prior therapies and procedures will be coded using MedDRA Version 24.0.

Prior medications, therapies, and procedures are defined as that with a start date prior to the date of the first dose of study drug.

The prior medication, therapy, and procedure usage will be summarized by the number and percentage of subjects in each treatment group and overall, within each preferred term for the Safety Analysis Set. Multiple uses of the same medication, therapy, or procedure by a subject in the same category will be counted only once.

All prior medications, therapies, and procedures will be listed for the Safety Analysis Set.

6.5. Concomitant Medications, Therapies, and Procedures

Concomitant medications will be coded using the WHO Drug Dictionary dated Sept 2021.

Concomitant medications, therapies, and procedures are defined as those with a start date prior to the date of the first dose of study drug and continuing on or after the first dose of study drug, or with a start date between the dates of the first and last doses of study drug, inclusive. Any medication, therapy, or procedure with a start date after the date of the last dose of study drug will not be considered a concomitant medication, therapy, or procedure.

The concomitant medication, therapy, and procedure and usage will be summarized by the number and percentage of subjects in each treatment group and overall, within each preferred term for the Safety Analysis Set. Multiple uses of the same medication, therapy, or procedure by a subject in the same category will be counted only once.

All concomitant medications, therapies, and procedures will be listed for the Safety Analysis Set.

6.6. Exposure to Study Drug

A data listing will be created giving the date and time of dose administration for each subject in the Safety Analysis Set.

6.7. Protocol Deviations

Protocol deviations will be identified and recorded by the site and tracked separately from the clinical database. Clinical team members on the Ironwood Study Execution Team (SET) will determine which protocol deviations are important protocol deviations (IPDs) and will categorize IPDs based on a blinded review of all protocol deviations prior to database lock and unblinding. The SET members reviewing the protocol deviations will include the study clinical operations lead, the medical director, the study biostatistician, and other personnel as appropriate.

The number and percentage of subjects with IPDs will be presented by treatment group and IPD category for the Safety Analysis Set. Protocol deviations and IPDs will be provided by subject in a data listing for the Safety Analysis Set.

A separate listing of all inclusion/exclusion criteria deviations will be provided for all randomized subjects (ie, the ITT Set).

7. SAFETY ANALYSIS

All safety parameters will be summarized using descriptive statistics. Safety analyses will be performed on the Safety Analysis Set. The safety parameters will include AEs, clinical laboratory evaluations, vital signs, and ECGs. For each laboratory parameters and ECG site interpretation, the last nonmissing assessment before the first dose of study drug will be used as the baseline for all analyses of that laboratory parameter or ECG interpretation. For numeric ECG measurements, the average of the last triplicate ECG before dosing will be used as baseline. For vital signs, the last supine measurement before dosing will be used as baseline.

All safety analyses will be performed according to the treatment actually received regardless of the allocated treatment. All subjects on placebo arm will be pooled from available cohorts, whenever appropriate, to conduct analyses.

7.1. Adverse Events

AEs will be coded by SOC and PT using MedDRA Version 24.0. The study investigator will assess the severity of the AE and assign a grade using the Common Terminology Criteria for Adverse Events (CTCAE). An AE is considered a treatment-emergent AE (TEAE) if the AE started after initial study drug administration and within 1 day of the last dose of study drug. In addition, an AE that started before initial study drug but worsened after the first dosing of the study drug is also considered a TEAE.

The number and percentage of subjects reporting TEAEs in each treatment group (or cohort) will be tabulated:

- by SOC and PT
- by SOC, PT, and CTCAE grade
- by SOC, PT, and relationship to study drug.

If a subject has more than 1 TEAE coded to the same PT, the subject will be counted only once for that PT by identifying the TEAE with the highest CTCAE grade and the closest relationship to study drug.

The incidence of the following TEAEs will be summarized by PT:

- Treatment-emergent Serious Adverse Events (TESAEs)

All AE summary tables will be sorted alphabetically by SOC and each PT within the SOC will be sorted by decreasing frequency for the IW-3300 group.

A TEAE summary table with all the non-SAEs by SOC and PT will be generated to support the clinicaltrials.gov reporting requirements.

AE listings will be presented for all subjects with AEs, all screened subjects with SAEs, all SAEs (regardless of treatment-emergent status), and subjects who died (if any), respectively.

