4.1.1.3. Follow-up Period

The Follow-up Period will start immediately after subjects are discharged from the Phase 1 CRU on Day 8 and will last until Day 21 (+3). On Day 21 (+3), the Phase 1 CRU will contact subjects for the Follow-up Phone Call (at the discretion of the investigator, subjects may be requested to return to the Phase 1 CRU for their follow-up contact). The Follow-up Phone Call will be considered the end of the study for that subject.

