9.4.2. Primary Endpoints Analyses

The primary endpoint analysis will be based on the Safety Analysis Set.

AE verbatim terms will be coded in the electronic data capture (EDC) system against the most current version of the Medical Dictionary for Regulatory Activities (MedDRA) available at the start of the study.

TEAEs are defined in Section 10.3.1. The TEAEs and TESAEs for 1 calendar day post last dose will be summarized by system organ class, preferred term, and treatment (or cohort).

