10.3.1.2. TEAE Definition

- A TEAE is an event that emerges, or a pre-existing event that worsens, any time after the initiation of the first dosing of the investigational product.

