11.1.3. Definition of Visit Windows

Study day will be calculated in accordance with CDISC standards defined in the SDTM and ADaM implementation guides. The date of first dose is defined as study day 1, and the day before is study day -1. Here are the formulas appear below:

- If the assessment date is on or after the date of first dose of study drug:
Study day = assessment date – date of first dose + 1
- If the assessment date is before the date of first dose of study drug:
Study day = assessment date – date of first dose

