11.1.4. Missing Date of Adverse Events

For AEs with partial start dates, nonmissing date elements, such as start year, will be used to determine if the AE is treatment-emergent or not. If a determination cannot be made using the nonmissing date elements as to when the AE occurred relative to study drug administration (eg, AE start day is missing and the year and month are the same as the year and month of the first dose of study drug), then the AE will be classified as treatment-emergent.

To facilitate categorization of AEs as treatment-emergent, the start date will be imputed. The stop date will be imputed if it is needed to determine whether an AE is treatment emergent.

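### SAP 7.1 ends the TEAE window for new-onset AEs but not for worsening of pre-dose AEs, so its tables depart from Protocol 9.4.2

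*SAP*

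**What the plan says.** Both primary endpoints are incidences, of TEAEs and of TESAEs (Protocol 3.3.1, SAP 3.3.1). Three passages decide which events count.

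- Protocol 10.3.1.2 defines a TEAE as an event that emerges or worsens "any time after the initiation of the first dosing of the investigational product". It sets no end date for either type.
- Protocol 9.4.2 points to that definition and then sets the summary window: "The TEAEs and TESAEs for 1 calendar day post last dose will be summarized by system organ class", preferred term and treatment. The limit covers all TEAEs, with no distinction between onset and worsening.
- SAP 7.1 builds the window into the definition. A new AE is a TEAE "if the AE started after initial study drug administration and within 1 day of the last dose of study drug". The following sentence says that "an AE that started before initial study drug but worsened after the first dosing of the study drug is also considered a TEAE", with no end limit.

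The incidence tables in SAP 7.1 (by SOC and PT, by CTCAE grade, by relationship, TESAEs, and the non-serious table for registry reporting) are restricted to TEAEs. The listings are wider: they cover all subjects with AEs and "all SAEs (regardless of treatment-emergent status), and subjects who died (if any), respectively".

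AEs are collected until early termination or the Follow-up Phone Call (Protocol 8.3.1), which falls on Day 21 with an allowance of 3 days (Protocol 4.1.1.3).

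**The concern.** A rule for a primary endpoint should treat like events alike and match the protocol's planned summary. SAP 7.1 does neither for events after the window. Its worsening sentence is a second, separate route into the tables, and nothing in it carries over the 1-day limit from the sentence before. A programmer who follows the SAP literally would tabulate a late worsening that Protocol 9.4.2 excludes, while leaving out a new SAE that starts on the same day.

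What is at stake is the consistency of a descriptive count. Safety and tolerability is the only primary objective, and each IW-3300 dose group has 6 subjects, so the rule for who is counted should leave no room for choice at the programming stage.

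**Working it through.** There is no sample size, power or error-rate figure to reproduce. The check is study-day arithmetic, followed by test cases put through each rule.

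**Inputs.** Dosing runs from Day 1 through Day 7 (Protocol 6.1.1). The follow-up call is on Day 21, at latest Day 24 (Protocol 4.1.1.3). Study day is date-based (SAP 11.1.3): "The date of first dose is defined as study day 1, and the day before is study day -1", and from first dose onward, study day = date − date of first dose + 1.

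**End of the window.** For a subject who takes all 7 doses, the last dose is on Day 7, so the next calendar day is 7 + 1 = Day 8. SAP 7.1 says only 1 day where Protocol 9.4.2 says 1 calendar day. The date-based study day in SAP 11.1.3 supports the calendar reading, but SAP 7.1 does not state it.

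**Test cases.** Does the event count?

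| Event | SAP 7.1 (TEAE, tabulated) | Protocol 10.3.1.2 (TEAE) | Protocol 9.4.2 (summarized) |
|---|---|---|---|
| New onset Day 5 or Day 8 | Yes | Yes | Yes |
| New onset Day 9 or Day 15 | No | Yes | No |
| Pre-dose AE worsens Day 5 | Yes | Yes | Yes |
| Pre-dose AE worsens Day 15 | **Yes** | Yes | **No** |

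For fully dated new-onset events, SAP 7.1 and Protocol 9.4.2 give the same tables. They part only in the last row.

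**Partial dates.** Under SAP 11.1.4, if the known date elements cannot place an AE relative to study drug administration, "then the AE will be classified as treatment-emergent". The example given is a missing day in the month of first dose. So a new Day 15 AE with a full date is left out, while the same AE with the day missing is counted if Day 15 falls in the month of first dose. The section's example concerns the first dose only, and no rule is stated for the end of the window. As an illustration, take a first dose on the 28th of a 30-day month. The last dose is 6 days later, on the 4th, and the window ends on the 5th. An AE known only to have started in that later month is certainly after first dose, but it cannot be placed before or after the 5th.

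**Collection time outside the window.**

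- Call on Day 21: 21 − 8 = 13 days, and 13/21 = 61.9%.
- Call on Day 24: 24 − 8 = 16 days, and 16/24 = 66.7%.

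These are shares of days from first dose, for subjects who take all 7 doses. They say nothing about the share of events.

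**The case against.** The strongest reply is that the 1-day cut is deliberate and appears in both documents. Late events are still collected, followed up and listed, and with 18 to 27 subjects each one can be read individually. Protocol 9.1 plans no hypothesis test, and under Protocol 6.6 the decision to move from Cohort 1 to Cohort 2 uses data through Day 8. The late-worsening route is also narrow: it needs an AE that began before first dose in a medically healthy subject, was still open after Day 8, and then worsened. A medical-history condition that deteriorates is itself recorded as an AE (Protocol 8.3.1). If its start is dated at the deterioration, which the documents do not state, the new-onset limit would already apply.

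All of this stands, and it sets the size of the point. It does not remove the mismatch in the worsening sentence. Three stronger readings are tempting, and the documents do not support them.

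- A reader might infer that the protocol contradicts itself. Sections 10.3.1.2 and 9.4.2 can be read together as an open-ended definition and a summary window.
- A reader might infer that the SAP understates incidence relative to the protocol, for example 0/6 against 1/6 = 16.7% when one subject's only event is a late new-onset AE. No document plans a table under 10.3.1.2 alone, and under 9.4.2 that subject is also counted as 0/6. The contrast shows only what one late event would do to an incidence if it were tabulated.
- A reader might infer that leaving late new-onset events out of the tables is an error. Both documents prespecify it, and the follow-up call is described as safety follow-up, not as a source for incidence tables.

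**Conclusion.** SAP 7.1 is wrong as written in one respect: worsening of a pre-dose AE has no end limit, whereas Protocol 9.4.2 limits the summary of all TEAEs and TESAEs to 1 calendar day after the last dose. The partial-date rule and the unqualified use of day in SAP 7.1 are small loose ends of the same definition.

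The severity is minor. Such late worsening should be uncommon in this population, every AE and SAE is listed, and no test or escalation decision changes. The documents give no rate of late events, so no expected number of affected subjects and no direction of bias can be stated.

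Separately, and not as an error, 62% to 67% of the days of AE collection after first dose feed no by-treatment table for fully dated new-onset events. This rests on all 7 doses being taken and on the calendar-day reading.

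**What to change.** Corrections:

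1. In SAP 7.1, apply one end limit to both routes. For example: *an AE is treatment-emergent for the summary tables if its onset, or the worsening of an AE present before first dose, occurs after first dosing and no later than the calendar day after the last dose*. This matches Protocol 9.4.2 and the date-based study day in SAP 11.1.3.
2. Add a note in the SAP that Protocol 10.3.1.2 is the open-ended definition and Protocol 9.4.2 the summary window.
3. Extend SAP 11.1.4 to say how a partial date is handled when it cannot be placed before or after the end of the window.

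These cost a few sentences. Step 1 needs the date on which an AE worsened. Protocol 10.3.1.3 asks for severity to be recorded as it changes, so I assume that date is available; this should be checked against the eCRF.

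Optional improvement: add one by-treatment table (incidence, CTCAE grade, relationship) of AEs and SAEs with onset or worsening after the window through the Day 21 (+3) call. It uses data already collected. The downside is that it will include some unrelated background events after discharge, counted under the same rule in every group.

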7.2. Clinical Laboratory Data

Descriptive statistics for clinical laboratory values (in SI units) and changes from baseline at each postbaseline time point will be presented by treatment group for each clinical laboratory parameter. All laboratory data will be listed for the Safety Analysis Set.

Table 1: Laboratory Assessments

Laboratory Assessments	Parameters			
Hematology	Platelet count	RBC Indices: MCV MCH MCHC % Reticulocytes	WBC Count with Differential: Neutrophils Lymphocytes Monocytes Eosinophils Basophils	
	RBC count			
	Hemoglobin			
	Hematocrit			
Clinical Chemistry	Blood urea nitrogen (BUN)	Potassium	AST	Total and direct bilirubin
	Creatinine	Sodium	ALT	Total protein
	Glucose	Calcium	Alkaline phosphatase	Magnesium
	Chloride	Albumin	Bicarbonate	Phosphate
	Cholesterol	Uric acid		
Inflammatory markers	
 • ESR (analyzed at an outside laboratory) • CRP 			
Hemoccult testing	
 • Point-of-care hemoccult test 			
Routine Urinalysis	
 • Specific gravity • pH, glucose, protein, blood, and ketones, by dipstick • Microscopic examination (if blood or protein is abnormal) • Urine culture (if urinary tract infection is suspected) 			
Other Screening Tests	
 • Drug and alcohol screen (to include at minimum: amphetamines, barbiturates, cocaine, opiates, cannabinoids, and benzodiazepines) • FSH • HCG (blood-based test at Screening and urine-based test at Check-in/Day -1) • SARS-CoV-2 testing (Screening and Check-in/Day -1) • HIV antibody and hepatitis panel (HBsAg, and HCV antibody) 			

For each clinical laboratory parameter, the number and percentage of subjects with potentially clinically significant (PCS) postbaseline clinical laboratory values will be tabulated by treatment group (or cohort). The criteria for PCS laboratory values are described in [Table 2](#). The percentages will be calculated relative to the number of subjects with non-PCS baseline values

and at least 1 postbaseline assessment. The numerator will be the total number of subjects who had non-PCS values at baseline and who had at least 1 postbaseline PCS value.

A supportive listing for subjects with PCS postbaseline values will be provided and will include the subject ID number, all lab values, both pre- and postbaseline, and a flag marking the PCS laboratory values.

Table 2: Criteria for Potentially Clinically Significant Laboratory Tests

Parameter	SI Unit	Lower Limit	Higher Limit
Chemistry			
Albumin	g/L	<0.9 × LLN	>1.1 × ULN
Alanine aminotransferase	U/L	—	≥3 × ULN
Alkaline phosphatase	U/L	—	≥3 × ULN
Aspartate aminotransferase	U/L	—	≥3 × ULN
Bicarbonate	mmol/L	<0.9 × LLN	>1.1 × ULN
Bilirubin, total	µmol/L	—	>1.5 × ULN
Calcium	mmol/L	<0.9 × LLN	>1.1 × ULN
Chloride	mmol/L	<0.9 × LLN	>1.1 × ULN
Cholesterol, total	mmol/L	—	>1.6 × ULN
Creatinine	µmol/L	—	>1.3 × ULN
Glucose	mmol/L	<0.8 × LLN	>1.4 × ULN
Magnesium	mmol/L	<0.9 × LLN	>1.1 × ULN
Phosphate	mmol/L	<0.9 × LLN	>1.1 × ULN
Potassium	mmol/L	<0.9 × LLN	>1.1 × ULN
Protein, total	g/L	<0.9 × LLN	>1.1 × ULN
Sodium	mmol/L	<0.9 × LLN	>1.1 × ULN
Urea nitrogen	mmol/L	—	>1.2 × ULN
Uric acid	µmol/L	<0.9 × LLN	>1.1 × ULN
Hematology			
Basophils, absolute cell count	10 ⁹ /L	—	>3 × ULN
Eosinophils, absolute cell count	10 ⁹ /L	—	>3 × ULN
Hematocrit	Ratio	<0.9 × LLN	>1.1 × ULN
Hemoglobin	g/L	<0.9 × LLN	>1.1 × ULN
Lymphocytes, absolute cell count	10 ⁹ /L	<0.8 × LLN	>1.5 × ULN
Mean corpuscular hemoglobin	Pg	—	>3 × ULN
Mean corpuscular hemoglobin concentration	g/L	—	>3 × ULN

Parameter	SI Unit	Lower Limit	Higher Limit
Mean corpuscular volume	fL	$<0.9 \times \text{LLN}$	$>1.1 \times \text{ULN}$
Monocytes, absolute cell count	$10^9/\text{L}$	—	$>3 \times \text{ULN}$
Neutrophils, absolute cell count	$10^9/\text{L}$	$<0.8 \times \text{LLN}$	$>1.5 \times \text{ULN}$
Platelet count	$10^9/\text{L}$	$<0.5 \times \text{LLN}$	$>1.5 \times \text{ULN}$
Red blood cell count	$10^{12}/\text{L}$	$<0.9 \times \text{LLN}$	$>1.1 \times \text{ULN}$
White blood cell count	$10^9/\text{L}$	$<0.7 \times \text{LLN}$	$>1.5 \times \text{ULN}$

LLN: Lower limit of normal value provided by the laboratory

ULN: Upper limit of normal value provided by the laboratory

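### SAP Table 2 flags MCH and MCHC only above 3 × ULN, with no lower limit, a level no plausible true value reaches, so those two PCS rows carry no information

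*SAP*

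**What the plan says.** SAP Section 7.2 tabulates, by treatment group or cohort, the number and percentage of subjects with a postbaseline PCS value for each laboratory parameter. The denominator is subjects who were not PCS at baseline and have at least one postbaseline assessment. The numerator is those among them with at least one postbaseline PCS value. Table 2 supplies the criteria.

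The two rows at issue are MCH, which reads "Mean corpuscular hemoglobin Pg — >3 × ULN", and "Mean corpuscular hemoglobin concentration", which reads in full "Mean corpuscular hemoglobin concentration g/L — >3 × ULN". The dash is the lower-limit column. The same pattern is used for basophils, eosinophils and monocytes.

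The quantities from which these indices are formed are treated differently: "Hemoglobin g/L <0.9 × LLN >1.1 × ULN" and "Hematocrit Ratio <0.9 × LLN >1.1 × ULN". The rows for "Red blood cell count" and "Mean corpuscular volume" also use 0.9 × LLN and 1.1 × ULN.

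The table footnote says where the limits come from: "ULN: Upper limit of normal value provided by the laboratory". No numerical reference range appears in either document, and neither gives a reason for 3 × ULN or another PCS criterion for these two indices.

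**The concern.** A multiple of 3 × ULN can suit a cell count or an enzyme, which can rise several-fold. MCH and MCHC are ratios: hemoglobin over red-cell count, and hemoglobin over hematocrit. They do not triple unless their components are grossly abnormal. If the limit is out of reach, the two rows will report 0% in every group because of how the rule is set. A reader of the table cannot tell that zero from one produced by a criterion capable of detecting a change. Safety is the primary objective, and laboratory evaluations are among the safety parameters named in SAP Section 7, so an empty row can be read as reassurance.

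**Working it through.** The plan has no figure to reproduce here. The check is whether the stated limit can be reached.

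**Inputs from SAP Table 2.** MCH and MCHC: flag if > 3 × ULN, no lower limit. Hemoglobin (Hb), red-cell count (RBC) and hematocrit (Hct): flag if < 0.9 × LLN or > 1.1 × ULN.

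**Assumed inputs (not in the documents).** MCH ULN 31–35 pg; MCHC ULN 340–370 g/L; Hb ULN 160–180 g/L; RBC LLN 3.7–4.3 × 10¹²/L; Hct LLN 0.34–0.39.

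**Step 1: the limit in absolute terms.**
- MCH: 3 × 31 = 93 pg to 3 × 35 = 105 pg.
- MCHC: 3 × 340 = 1020 g/L to 3 × 370 = 1110 g/L, that is, more than 1 kg of hemoglobin per litre of packed red cells.

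**Step 2: distance from ordinary values.** Treat a reference range as mean ± 1.96 SD, and take the wider of the ranges tried.
- MCH 26–34 pg: (3 × 34 − 30) / (8 / 3.92) = 35 SD above the mean.
- MCHC 310–370 g/L: (3 × 370 − 340) / (60 / 3.92) = 50 SD above the mean.

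**Step 3: the largest index possible with no component flagged.** Put Hb at 1.1 × ULN and RBC or Hct at 0.9 × LLN, crossing the extremes of the assumed ranges.

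| Index as a multiple of its ULN | Smallest | Largest |
|---|---|---|
| MCH = (1.1 × Hb ULN) / (0.9 × RBC LLN) / MCH ULN | 176 / 3.87 / 35 = 1.30 | 198 / 3.33 / 31 = 1.92 |
| MCHC = (1.1 × Hb ULN) / (0.9 × Hct LLN) / MCHC ULN | 176 / 0.351 / 370 = 1.36 | 198 / 0.306 / 340 = 1.90 |

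Both stay at about 1.3–1.9 × ULN, against a limit of 3.

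**Step 4: what a flag would require.** With Hb at 140 g/L:
- MCH: RBC below 140/105 = 1.33 to 140/93 = 1.51 × 10¹²/L. The RBC row would already flag below 0.9 × 3.7 = 3.33 to 0.9 × 4.3 = 3.87.
- MCHC: Hct below 140/1110 = 0.126 to 140/1020 = 0.137. The Hct row would already flag below 0.9 × 0.34 = 0.306 to 0.9 × 0.39 = 0.351.

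**Step 5: the other direction.** With no lower limit, no fall in either index, of any size, is flagged.

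**The case against.** The strongest reply is that little depends on these rows, and most of it stands.

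- SAP Section 7.2 gives MCH and MCHC descriptive statistics and changes from baseline at each postbaseline time point, and lists all laboratory data. A shift either way would be visible there.
- Hemoglobin, hematocrit, red-cell count and MCV have two-sided limits.
- The investigator must review every laboratory report and record clinically relevant changes as adverse events (Protocol 8.2.4), whatever Table 2 says.
- The primary endpoints are TEAEs and TESAEs. The suspension criteria in Protocol 7.1.1 rest on related SAEs and CTCAE-graded events. The Dose Escalation Committee reviews laboratory results, but nothing ties its decision to PCS flags. No hypothesis test is planned.
- A one-sided limit is not an error in itself. ALT, AST, alkaline phosphatase, bilirubin, cholesterol, creatinine and urea nitrogen are one-sided too.

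A reader might also infer three stronger things that the documents do not support.

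- **That a flag is strictly impossible.** Step 3 holds only while the components are within their own limits, so by itself it shows that a flag would be redundant. Unreachability rests on the absolute levels in Steps 1 and 2, and a spurious result or unit error could still produce a flag.
- **That the limit was copied from the white-cell rows.** The pattern matches, but neither document says how it was chosen.
- **That the rule hides a safety signal.** The other outputs listed above would show one.

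None of this makes the two rows informative as written.

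**Conclusion.** The point holds as a minor defect in a descriptive table. Across the whole span of assumed reference limits, the criterion lies beyond any plausible true value in up to 27 healthy subjects dosed for 7 days. The expected entry is therefore 0% in every group, and that zero says nothing about red-cell indices. The numbers depend on assumed reference ranges, because the laboratory's are not given, but the conclusion does not change anywhere within them. No safety conclusion and no stated dosing rule in the trial turns on it.

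**What to change.** Before database lock, do one of the following.

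1. **Set both rows to < 0.9 × LLN and > 1.1 × ULN**, matching MCV and the other red-cell rows. Under the assumed ULNs the upper limits become 1.1 × 31 = 34.1 to 1.1 × 35 = 38.5 pg for MCH, and 1.1 × 340 = 374 to 1.1 × 370 = 407 g/L for MCHC. A fall could then be flagged as well. Table 2 uses other multiples elsewhere, so this pair is a choice made for consistency; no other text in the documents requires it.
2. **Delete both rows from the PCS table** and rely on the summaries and listings. Table 2 already omits one index listed in SAP Table 1, % reticulocytes.

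The cost is four table cells or two deleted rows. Under the first option a few subjects may be flagged; the documents give no basis for predicting how many, and it may be none. SAP Section 2 requires deviations from the final approved plan to be noted in the clinical study report, so an earlier correction is simpler.
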